Infusion-related reaction (IRR) is a listed side effect of xentuzumab treatment. There have been 3 serious IRRs reported. One event was Grade 3 or higher. All events recovered with management per protocol. Only 1 patient discontinued the study due to an infusion-related reaction. Infusions of xentuzumab should be administered under close supervision of a medically qualified staff member with availability of resuscitation facilities. As mannitol is

used in the formulation of xentuzumab, infusion durations of less than one hour should be avoided. Following each infusion, a one hour observation period is recommended.

Infusion reactions will be graded and treated following standard of care or local guidance in this trial.

Although rare, a potential for drug-induced liver injury (DILI) is under constant surveillance by sponsors and regulators. Therefore, this trial requires timely detection, evaluation, and follow-up of laboratory alterations in selected liver laboratory parameters to ensure patients' safety, see also [Section 5.3.6.1](#).

More information about the known and expected benefits, risks, and reasonably anticipated adverse events (AEs) of abemaciclib and xentuzumab may be found in the Investigators' Brochures (IBs) (see current versions). Information on AEs expected to be related to the investigational product may be found in Section 7 of the IBs. Information on serious adverse events (SAEs) expected in the study population independent of drug exposure and that will be assessed by the sponsor in aggregate, periodically during the course of the study, may be found in Sections 6 (Effects in Humans) of the IBs.

The sponsor, monitor, and investigators will perform this study in compliance with the protocol, good clinical practice (GCP) and International Conference on Harmonisation (ICH) guidelines, and applicable regulatory requirements.

During the trial, investigators are advised to manage treatment-related side-effects proactively. Suggested supportive care measures for the management of treatment related AEs and instructions for dose reductions for individual patients are provided in [Section 4.4](#)

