4.4.2 Management and grading of infusion reactions

The xentuzumab infusion should always be administered under close supervision of a medically qualified staff member with immediate availability of appropriate resuscitation facilities.

Infusion reactions may occur during infusion with xentuzumab and include pyrexia, chills, rigors, dyspnoea, urticaria, bronchospasm, hypotension and hypertension. **A one hour observation period is recommended following each infusion.** If there is no infusion reaction during the first treatment course, the observation period following xentuzumab infusion may be adjusted at the discretion of the investigators. Mild to moderate infusion reactions may be managed with a slower infusion rate and prophylactic antihistamines for subsequent dosing. Severe reactions require immediate and permanent discontinuation of infusion. The hypersensitivity reactions will be graded according to the National Cancer Institute (NCI) Common Terminology Criteria for Adverse Events (CTCAE) version 4.03 ([R10-4848](#)).

The infusion duration may be extended to over one hour and up to a maximum of three hours.

The infusion reactions should be treated symptomatically as judged clinically relevant by the investigator. For symptomatic treatment of infusion reactions: hydrocortisone, antihistamines such as chlorphenamine accompanied by an antipyretic/analgesic and/or a bronchodilator is recommended.

Infusion reactions will not be reported on the standard AE page but will be reported on a separate page specifically for infusion reactions in the CRF.

Table 4.4.2: 1 Infusion reaction management

Infusion Reaction Grade	Management
CTCAE Grade 1 or 2	In the event of a CTCAE grade 1 infusion reaction, the infusion rate should be reduced by 50%. A Grade 2 infusion reaction may require symptomatic treatment, as described above (with infusion interruption). Once the event has resolved, the infusion may be restarted at the reduced rate.
CTCAE Grade 3	For patients experiencing a CTCAE grade 3 infusion reaction, infusion should be interrupted immediately and patients should receive aggressive symptomatic treatment, as described above. Only after all the symptoms have disappeared, the infusion may be re-started if it is within 3 hours since the infusion start. The infusion rate should be reduced by half after re-start

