Protocol-specified AESIs are specified in the CTP Section 5.3.6.1. Their incidence will also be reported. DLTs are considered as AESIs only in the dose finding cohorts.

Adverse events by user defined AE categories (UDAEC)

User defined adverse events categories (UDAEC) as defined on project level by the pharmacovigilance working group will be derived and the latest version will be used for the analysis. Details of the current version are presented below in the table below.

Table 7.8.1: 1 Adverse events by user defined AE categories

SSC	Group[#]
Hepatic impairment	Drug related hepatic disorders – comprehensive search (SMQ)
Hyperglycaemia narrow	Hyperglycaemia/new onset diabetes mellitus (SMQ) - narrow
Infusion related reaction	Hypersensitivity (SMQ) - broad
Non-infectious pneumonitis	Interstitial lung disease (SMQ) - narrow
Renal insufficiency	Acute renal failure (SMQ) - broad and narrow; Proteinuria (SMQ)-broad and narrow; Glomerulonephritis and nephrotic syndrome:HLT
Weight loss	Weight loss (BIcMQ) – broad and narrow
Neutropenia	Haematopoietic leukopenia (SMQ) – narrow
Stomatitis	Stomatitis (BIcMQ) – broad and narrow
Asthenia	MedDRA PTs: Asthenia, Fatigue, Lethargy, Malaise, and Decreased activity
Haemorrhage	Haemorrhage laboratory terms (SMQ)-narrow; Haemorrhage terms (excl laboratory terms) (SMQ)-broad and narrow
Anemia	Haematopoietic erythropenia (SMQ) – broad and narrow
Thrombocytopenia	Haematopoietic thrombocytopenia (SMQ) - narrow
Thromboembolism	Embolic and thrombotic events, vessel type unspecified and mixed arterial and venous (SMQ)-broad and narrow
Bradycardia	Torsade de pointes/QT prolongation (SMQ), PT of Bradycardia
Rash	BIcMQ: Skin eruptions (subsearch2: Skin rash potentially related to drug use [broad and narrow])

[#] This column indicates whether the Term(s) provided in the first column are MedDRA preferred terms (**PT**), Standardised MedDRA Queries (**SMQ**) or BI customised MedDRA Queries (**BIcMQ**).

The incidence of AE by UDAEC will be analysed.

Proprietary confidential information © 2021 Boehringer Ingelheim International GmbH or one or more of its affiliated companies

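### The SAP's infusion-related-reaction row is a broad hypersensitivity search with no link to a xentuzumab infusion, so it can count events that occur when no infusion is being given

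*SAP*

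**What the plan says.** Table 7.8.1:1 in SAP 7.8.1 lists the user-defined AE categories. The row for infusion related reaction has one entry, "Hypersensitivity (SMQ) - broad". Under the table the SAP adds "The incidence of AE by UDAEC will be analysed". The definitions are not specific to this trial: "User defined adverse events categories (UDAEC) as defined on project level by the pharmacovigilance working group will be derived", and the latest version is used.

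Protocol 4.4.2 describes the reactions by their relation to the infusion: "Infusion reactions may occur during infusion with xentuzumab and include pyrexia, chills, rigors, dyspnoea, urticaria, bronchospasm, hypotension and hypertension". It has them graded by CTCAE version 4.03 and fixes where they are entered: "Infusion reactions will not be reported on the standard AE page but will be reported on a separate page specifically for infusion reactions". Protocol 2.3 explains why they matter: "Infusion-related reaction (IRR) is a listed side effect of xentuzumab treatment".

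Three counting rules apply to the row:
- **Window.** SAP 7.8.1 treats an AE as on treatment from first drug intake, run-in included, to the end of the residual effect period. SAP 6.1 sets that period at 42 days.
- **Set.** SAP 6.3 admits a patient to the treated set after a single dose of any trial drug, run-in included.
- **Denominator.** SAP 7 generally bases percentages on everyone in the set.

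**The concern.** The row carries the name of a reaction defined by the xentuzumab infusion, but what it counts does not depend on an infusion. The trial already has a purpose-built, CTCAE-graded record of these reactions, and the visible SAP does not mention it.

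Infusion reaction is an adverse reaction attributed to the investigational antibody, and this row is the only output under that name in the visible SAP. It is not a protocol AESI (protocol 5.3.6.1), and it is excepted from the catch-all item for other Grade 3 or higher non-haematological toxicities in the DLT list (protocol 5.3.7). A reader of the trial report would take the row as the infusion-reaction rate for xentuzumab. If it also holds events that began with no xentuzumab being given, it does not estimate that rate.

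**Working it through.** The plan gives no figure to reproduce. The check sets the rules side by side, then works out what one patient is worth.

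**1. Can an event count with no infusion given?** An event enters the row if it matches the search and starts in the on-treatment window. Two stretches of that window contain no xentuzumab:
- *Run-in.* Protocol 6.2.1 gives cohort E 9 days of abemaciclib before the first xentuzumab infusion, and SAP 7.8.1 counts the run-in as on treatment. The SAP also names cohort F here, but protocol 6.2.1 now limits the run-in to cohort E, so only E is used.
- *After xentuzumab stops.* Protocol 4.1.4.2 lets a patient stay on the remaining drugs when one is permanently stopped. Protocol 3.3.4.2 foresees continued abemaciclib and fulvestrant. Protocol 2.3 and 4.1 record the sponsor's recommendation of 19 October 2021 to stop xentuzumab at once. SAP version 2.0 is dated 25 October 2021, six days later. The 42 days run from the last dose of trial medication, so the window stays open while abemaciclib continues.

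In both stretches a matching event would be tabulated as an infusion reaction. This follows from the rules alone and needs no knowledge of which terms the search contains.

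**2. Does the denominator fit?** A cohort E patient who takes abemaciclib in the run-in and never receives xentuzumab is in the treated set, and so in the denominator, but could not have had an infusion reaction. The effect is small. Assuming one such patient among 20 and one true reaction, the rate is 1/20 = 5.0% instead of 1/19 = 5.3%.

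**3. Can true reactions be missed?** Protocol 4.4.2 keeps them off the standard AE page. SAP 7.8.1 speaks of AE data on the CRF and names no page. Protocol 5.3.6.2 has AEs documented on whichever eCRF is appropriate. Together these allow the infusion-reaction page to be merged into the AE data but do not say that it is. The visible text leaves the question open.

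**4. What is one patient worth?** The planned sizes are 30 each in D1 and D2 and 20 each in E and F (protocol 7.7). The shift from *k* misclassified patients among *n* is *k*/*n*:
- *n* = 30: 1/30 = 3.3 points per patient.
- *n* = 20: 1/20 = 5.0 points per patient.

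The documents do not give *k*, so the total error and its net direction cannot be computed.

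**The case against.** The strongest reply is that a separate entry page need not mean a separate dataset. Protocol 4.4.2 is a data-entry instruction, nothing confines the AE tables to the standard page, and a merge would put every infusion reaction into the AE data. This stands against one tempting inference, that the reactions are missing from the AE tables. The documents do not show that. It does not answer step 1, because a merge would leave the row without an infusion condition.

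Second, protocol 4.4.2 itself uses the word hypersensitivity when it says how these reactions are graded, and it lists urticaria and bronchospasm among the signs. The search is therefore related to the target, and calling it plainly wrong would go too far. A reader might also infer that it misses some of the listed signs or takes in unrelated skin events. Its contents are not in the documents, so neither can be asserted. Nor is a patient appearing in both this row and the Rash row an error: SAP 7.8.1 counts patients, and nothing says the categories exclude one another.

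Third, the category is set at project level, safety analyses are descriptive, and other planned tables (by preferred term, serious events, events leading to xentuzumab discontinuation) may show these reactions. All true, and this limits the consequences. But a trial-level summary can be added without altering the project category, and those other tables do not give an infusion-reaction rate.

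Finally, parts of the SAP are not visible and it refers to a technical TSAP that is not available, so a dedicated output may exist. That is why the under-count is put as an open question.

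**Conclusion.** The point holds for the over-count. As written, the row can include events from cohort E's run-in and from time after xentuzumab is stopped, and its percentages rest on a set that does not require an infusion. An under-count is possible but not shown. One misclassified patient is worth 3.3 points in D1 or D2 and 5 points in E or F at the planned sizes. How many there would be depends on how many matching events fall in those stretches, which the documents do not give.

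A reader might conclude that the reported rate is known to be wrong, or that infusion reaction is xentuzumab's only listed side effect. Neither is supported: the size and net direction of any error are unknown, and protocol 2.3 calls it one listed effect without saying there are no others. The consequence is confined to descriptive safety reporting, and no primary endpoint is touched. The change is still worth making, because it is cheap and gives the row the meaning its label claims.

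**What to change.** In SAP 7.8.1:
- Derive the infusion-related-reaction summary from the dedicated infusion-reaction CRF page: patients with any reaction, and worst CTCAE grade.
- Use patients given at least one xentuzumab infusion as the denominator.
- State whether the records from that page are included in the overall AE tables.
- Report the result of the hypersensitivity search as a supplementary row named Hypersensitivity.

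The protocol already provides for collection of the data. The cost is a few sentences in the SAP, the programming, and one extra output beside the project-level category.

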2.3 BENEFIT - RISK ASSESSMENT

There is a high unmet medical need for patients with advanced or metastatic HR+ BC and NSCLC, as described in [Sections 1.1](#) and [2.1](#). Both abemaciclib and xentuzumab have shown encouraging preliminary anti-cancer activity in early-phase clinical trials.

Therefore, and because this trial will enrol patients without curative therapeutic options, it is believed that patients with solid tumours, NSCLC or HR+ BC treated with xentuzumab plus abemaciclib with or without hormonal background therapy at standard doses will have better efficacy (clinical benefit) compared to abemaciclib with or without hormonal background therapy alone.

Abemaciclib

Hematologic toxicities including neutropenia, leukopenia, anaemia, and thrombocytopenia have been observed in patients treated with abemaciclib, and causality has been established. Patients will therefore be monitored closely for signs of infection, anaemia, and bleeding.

Gastrointestinal toxicities including diarrhoea, nausea, and vomiting have been observed in patients treated with abemaciclib, and causality has been established. Patients will therefore be monitored closely for gastrointestinal side effects. Patients with these symptoms will be evaluated promptly, treated supportively, and monitored closely for sequelae such as dehydration. Because diarrhoea possibly related to abemaciclib has been manageable with standard antidiarrheal agents such as loperamide, early treatment of diarrhoea is recommended in this trial.

Xentuzumab

As of 18 January 2019, xentuzumab was well tolerated in clinical trials, with no relevant specific side effects reported. The type and pattern of adverse events (AEs) observed to date have generally been of mild to moderate intensity (CTCAE Grades 1 or 2) or consistent with the safety profile of combination backbone treatment or consistent with the underlying neoplastic conditions of patients enrolled on the study. The most frequently reported AEs for xentuzumab monotherapy were fatigue, decreased appetite, nausea, diarrhoea, and vomiting.

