4.4.5 Venous Thromboembolism

Venous thromboembolic events were reported in patients receiving abemaciclib plus fulvestrant or aromatase inhibitors in breast cancer studies. The majority of the events were non-serious and were treated with low-molecular-weight heparin. Generally, these events did not result in discontinuation of the study treatment. At this time, the mechanism underlying the association between abemaciclib and the occurrence of VTEs is not known. Monitor patients for signs and symptoms of deep vein thrombosis and pulmonary embolism and treat as medically appropriate.

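### The SAP's Thromboembolism category, as printed, lists no venous search, although venous thromboembolism is the abemaciclib risk the protocol names

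*SAP*

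**What the plan says.** SAP section 7.8.1 plans an incidence table by user-defined adverse event categories. The categories are set at project level by the pharmacovigilance working group, and Table 7.8.1:1 prints the version then current. The Thromboembolism row has a single entry: "Embolic and thrombotic events, vessel type unspecified and mixed arterial and venous (SMQ)-broad and narrow".

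Where a category is built from several searches, the table lists each one. The Haemorrhage row reads "Haemorrhage laboratory terms (SMQ)-narrow; Haemorrhage terms (excl laboratory terms) (SMQ)-broad and narrow", and the Renal insufficiency row lists three components in the same way.

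The SAP adds that the categories "will be derived and the latest version will be used for the analysis".

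Protocol section 4.4.5, headed Venous Thromboembolism, states: "Venous thromboembolic events were reported in patients receiving abemaciclib plus fulvestrant or aromatase inhibitors in breast cancer studies". It then instructs investigators: "Monitor patients for signs and symptoms of deep vein thrombosis and pulmonary embolism and treat as medically appropriate".

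**The concern.** A row labelled Thromboembolism will be read as the thromboembolism result for the combination. The risk the protocol describes is specifically venous, while the search behind the row is limited by its own title to events of unspecified or mixed vessel type. A deep vein thrombosis is neither by that description, and the protocol places pulmonary embolism under the same venous heading.

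Most of the trial's patients are exposed to the combination in question. Cohorts D, F, D1 and D2 receive abemaciclib with fulvestrant, and cohorts B and C receive it with an aromatase inhibitor. If the row is programmed as printed, it could show few or no patients in a cohort where some had venous events, and nothing in the label would warn the reader.

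**Working it through.** The SAP states no figure for this category, so there is none to reproduce. The check is a comparison of texts, followed by simple arithmetic on what one patient is worth.

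**Step 1: what the row searches.** One search is listed, covering unspecified and mixed vessel types in both its broad and narrow scopes. No venous or arterial search is listed.

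**Step 2: is the entry shorthand for a wider search?** The table's own practice suggests not. Haemorrhage shows two components and Renal insufficiency three, separated by semicolons. A single entry therefore reads as the whole definition.

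**Step 3: does another row pick up venous events?** The table has 15 rows. The other 14 cover hepatic impairment, hyperglycaemia, infusion related reaction, non-infectious pneumonitis, renal insufficiency, weight loss, neutropenia, stomatitis, asthenia, haemorrhage, anaemia, thrombocytopenia, bradycardia and rash. None is directed at venous thrombosis or embolism.

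**Step 4: is there another grouped summary?** The adverse events of special interest in protocol section 5.3.6.1 are hepatic injury, dose-limiting toxicity in the dose finding cohorts, and pneumonitis. Venous thromboembolism is not among them. The Thromboembolism row is therefore the only grouped summary of these events visible in the SAP.

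**Step 5: timing.** Protocol section 4.4.5 was added by Global Amendment 4, dated 09 Apr 2019. SAP version 2.0, dated 25-Oct-21, lists all sections as changed. The printed row therefore postdates the protocol's statement of the risk by more than two years.

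**Step 6: size.** SAP section 7.8.1 counts patients, not events. Let n be the number of treated patients in a cohort and v the number whose only thromboembolic event is venous and lies outside the search. The category is then understated by v/n. Planned cohort sizes come from protocol section 7.7.

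| v | D1 or D2 (n = 30) | F (n = 20) |
|---|---|---|
| 0 | 0 points | 0 points |
| 1 | 1/30 = 3.3 points | 1/20 = 5 points |
| 2 | 2/30 = 6.7 points | 2/20 = 10 points |
| 3 | 3/30 = 10 points | 3/20 = 15 points |

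The documents give no rate of venous events, so v is an assumption and the table shows only what each value would mean. A patient who also has an event inside the search is counted anyway and does not add to v.

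**The case against.** Three points on the other side have weight.

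- **The term list is not printed.** What the search contains is inferred from its title. A reader might infer that every deep vein thrombosis and pulmonary embolism is certain to be missed. The documents do not establish that. For pulmonary embolism in particular, the only support is that the protocol discusses it under a venous heading, which does not show how the search classifies it. The supportable statement is that these events fall outside the search as titled, subject to confirmation.
- **The printed table is not the last word.** The SAP commits to the latest project-level version, and that version may already include a venous search. Nothing in the documents says that it does, so this makes the finding conditional without removing it. It also means that editing the SAP table alone might not change the analysis.
- **The events are not lost.** SAP section 7.8.1 tabulates all adverse events by system organ class and preferred term, with separate tables for serious, drug-related and fatal events and for those leading to dose reduction or discontinuation. In cohorts of 20 to 30 patients a careful reader can find venous events there. The analysis is descriptive, and nothing in the plan ties an endpoint or stopping rule to this category. Protocol section 4.4.5 also describes most reported events as non-serious and generally not leading to discontinuation. This limits the harm to a misleading grouped figure. It does not justify the figure, since the purpose of a grouped row is to bring separate terms together.

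A reader might also infer the same fault in two neighbouring rows. The documents do not support that:

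- Neutropenia is defined by "Haematopoietic leukopenia (SMQ) – narrow", while protocol section 2.3 lists neutropenia and leukopenia separately ("Hematologic toxicities including neutropenia, leukopenia, anaemia, and thrombocytopenia have been observed in patients treated with abemaciclib"). At most that is a broad search under a narrow label. Nothing shows that a neutropenia event would be lost.
- Infusion related reaction uses a hypersensitivity search, while protocol section 4.4.2 says: "Infusion reactions will not be reported on the standard AE page but will be reported on a separate page specifically for infusion reactions". The same section, however, refers to these reactions as hypersensitivity reactions when it describes their grading. Neither document says that records from the separate page are left out of the coded adverse event outputs.

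**Conclusion.** The point holds for the Thromboembolism row as printed. Its one listed search does not, by title, cover the venous events that protocol section 4.4.5 identifies with abemaciclib plus endocrine therapy, and no other row does.

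The only grouped thromboembolism incidence visible in the SAP can therefore understate a named risk, by 3.3 points in D1 or D2 and 5 points in F for each patient whose only such event is venous. This rests on three assumptions:

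- the search contains what its title says;
- the latest project-level version has not added a venous search;
- the treated cohorts are close to their planned sizes.

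The consequence is a potentially misleading row in a descriptive safety table. It is worth correcting because the risk is named in the protocol and the remedy is cheap.

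**What to change.** In Table 7.8.1:1, and in the project-level category definition that governs the analysis, list the venous embolic and thrombotic search beside the present one. Add the arterial search too if the row is meant to cover all thromboembolism. Preferably also show a separate Venous thromboembolism row, so that the risk in protocol section 4.4.5 has its own incidence. Before database lock, check the combined definition against the term list of the MedDRA version used, confirm that deep vein thrombosis and pulmonary embolism terms are captured, and record in the SAP which project-level version was applied.

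No new data are needed. The cost is a change of table wording, a re-run of standard adverse event outputs, and the possibility that the reported rate becomes less favourable.
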